**Table 12-3 Threshold Analysis Criteria for Laboratory Tests (as applicable)**

Parameter	Threshold Analysis	Comments
Coagulation		
Activated partial thromboplastin time (PTT)	>ULN - $\leq 1.5 \times \text{ULN}$ >1.5 - $\leq 2.5 \times \text{ULN}$ >2.5xULN	CTCAE grade 1-3
Prothrombin time (PT) International Normalized Ratio (INR)	>ULN - $\leq 1.5 \times \text{ULN}$ >1.5 - $\leq 2.5 \times \text{ULN}$ >2.5 x ULN	CTCAE grade 1-3

**Table 12-4 Threshold Analysis Criteria for ECGs**

Parameter	Threshold Analysis	Comments
HR	Bradycardia  <50 bpm <45 bpm Decrease from baseline $\geq 10$ bpm Decrease from baseline $\geq 20$ bpm <50 bpm and decrease from baseline $\geq 10$ bpm <50 bpm and decrease from baseline $\geq 20$ bpm	Per HV grade 2, 3, plus shift change
	Tachycardia  >100 bpm >115 bpm >130 bpm Increase from baseline $\geq 10$ bpm Increase from baseline $\geq 20$ bpm >100 bpm and increase from baseline $\geq 10$ bpm >100 bpm and increase from baseline $\geq 20$ bpm	
PR	$\geq 240$ ms $\geq 300$ ms $\geq 200$ ms and increase from baseline $\geq 40$ ms $\geq 200$ ms and increase from baseline $\geq 100$ ms	
QRS	>110 ms >160 ms Increase from baseline $\geq 20$ ms Increase from baseline $\geq 40$ ms	
QTc	>450 to <500ms (Male) or >470 to <500ms (Female) $\geq 500$ ms	To be applied to any kind of QT correction formula.
	Increase from baseline Increase from baseline >10 ms Increase from baseline >20 ms Increase from baseline >40 ms Increase from baseline >60 ms	

**Table 12-5 Threshold Analysis Criteria for Vital Signs**

Parameter	Threshold Analysis	Comments
Pulse Rate	Same as above in ECG category	
SBP increased	>140 mmHg >160 mmHg >10 mmHg increase from baseline >20 mmHg increase from baseline  >140 mmHg & >10 mmHg increase from baseline >140 mmHg & >20 mmHg increase from baseline >160 mmHg & >10 mmHg increase from baseline >160 mmHg & >20 mmHg increase from baseline	809/770 analyses
SBP decrease	<90 mmHg <80 mmHg >10 mmHg decrease from baseline >20 mmHg decrease from baseline  <90 mmHg and >10 mmHg decrease from baseline <90 mmHg and >20 mmHg decrease from baseline <80 mmHg and >10 mmHg decrease from baseline <80 mmHg and >20 mmHg decrease from baseline	Per HV grade 1, 3, plus shift change
DBP increased	>90 mmHg >100 mmHg >5 mmHg increase from baseline >10 mmHg increase from baseline  >90 mmHg and >5 mmHg increase from baseline >90 mmHg and >10 mmHg increase from baseline >100 mmHg and >5 mmHg increase from baseline >100 mmHg and >10 mmHg increase from baseline	
DBP decreased	<60 mmHg <45 mmHg >5 mmHg decrease from baseline >10 mmHg decrease from baseline  <60 mmHg and >5 mmHg decrease from baseline <60 mmHg and >10 mmHg decrease from baseline <45 mmHg and >5 mmHg decrease from baseline <45 mmHg and >10 mmHg decrease from baseline	
Weight	Weight gain ≥5 % increase from baseline ≥10 % increase from baseline ≥20% increase from baseline  Weight loss ≥5 % decrease from baseline ≥10 % decrease from baseline ≥20% decrease from baseline	CTCAE grade 1-3  CTCAE grade 1-3

**Table 12-6 Threshold Analysis Criteria for Laboratory Tests (for labeling purpose)**

Parameter	Threshold Analysis	Comments
Clinical Chemistry (LFT)		
ALT or AST	>3xULN >5xULN >8xULN	For labeling purpose

## **5.2 Efficacy Analysis**

### **5.2.1 Analysis of Endpoints Based on the Number of Clinical Events**

Number of Pulmonary Exacerbation (PEX) through Week 24: The analysis pre-specified in the protocol based on the negative binomial regression model will be performed first. If the negative binomial regression does not converge, the analysis will be performed using the Poisson regression with the same covariates and offset.

Note: If the number of events is less than 5 in either treatment group, neither the negative binomial regression nor the Poisson regression will be performed and analysis of event counts will be based on a Fisher's Exact test.

Analysis of the number of PEX requiring hospitalization and/or IV antibiotics therapy, the number of planned hospitalizations for CF, and the number of unplanned hospitalizations for reasons other than antibiotic therapy for sinopulmonary signs/symptoms will be performed in the same manner.

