### 7.2 Sample Size and Power

Approximately 360 subjects will be enrolled and randomized (1:1) to the VX-659/TEZ/IVA arm or the triple placebo arm. This sample size was determined to provide adequate power for the key secondary endpoint of the number of PEX through Week 24. Information regarding the powering of primary and selected key secondary endpoints is provided below.

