### **Power for Selected Secondary Endpoints**

A key secondary endpoint is the absolute change in ppFEV1 from baseline through Week 24. Assuming a within-group SD of 7 percentage points and a 10% dropout rate at Week 24, a sample size of 180 subjects in each treatment group will have approximately 99% power to detect a difference between the treatment groups of 5.0 percentage points for the absolute change in ppFEV1 from baseline through Week 24, based on a 2-sided, 2-sample *t*-test at a significance level of 0.05.

A key secondary endpoint is the number of PEx through Week 24. Assuming a rate of PEx for the placebo group of 0.6 over 24 weeks and a 10% dropout rate, with 180 subjects and the overdispersion parameter of 0.5 in each treatment group, the power to detect a 40% reduction in the PEx rate for VX-659/TEZ/IVA group compared to placebo group is approximately 80%, based on a 2-sided, 2-sample negative binomial regression model test for the ratio of rates, at a significance level of 0.05.

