### 9.3.2.2 Analysis Method

Absolute change in ppFEV1 through Week 24: Analysis of this variable will be based on an MMRM that is exactly the same as the primary efficacy variable. However, the Day 15 Visit will not be included in the estimation of the average treatment effect through Week 24 as the treatment effect is not expected to reach the steady state at Day 15.

Number of PEx through Week 24: Analysis of this variable will be performed using a negative binomial regression model with a fixed effect for treatment, as well as continuous baseline ppFEV1, age at screening (<18 versus ≥18 years of age), and sex (male versus female) as covariates. The logarithm of the subject-specific PEx analysis period duration (in years) will be treated as the offset in the model.

Absolute change in SwCl from baseline through Week 24: Analysis of this PD variable will be based on an MMRM similar to the analysis of the primary efficacy variable. Data obtained from Week 4, Week 8, Week 12, and Week 24 Visits will be included in the model and all of these visits will be included in the estimation of the average treatment effect through Week 24.

Absolute change in the CFQ-R respiratory domain score from baseline through Week 24: Analysis of this domain will be based on an MMRM similar to the analysis of the primary efficacy variable. Data obtained from Week 4, Week 8, Week 12, Week 16, and Week 24 Visits will be included in the model and all of these visits will be included in the estimation of the average treatment effect through Week 24.

Absolute change in BMI from baseline at Week 24: Analysis of this variable will be based on an MMRM similar to the analysis of the primary efficacy variable. Data obtained from Day 15, Week 4, Week 8, Week 12, Week 16, and Week 24 Visits will be included in the model.

Absolute change in SwCl from baseline at Week 4: Analysis of this PD variable will be based on an MMRM similar to the analysis of the primary efficacy variable. Data obtained from Week 4, Week 8, Week 12, and Week 24 Visits will be included in the model to estimate the treatment effect at Week 4.

Absolute change in CFQ-R respiratory domain score from baseline at Week 4: Analysis of this domain will be based on an MMRM similar to the analysis of the primary efficacy variable.

Data obtained from Week 4, Week 8, Week 12, Week 16 and Week 24 Visits will be included in the model to estimate the treatment effect at Week 4.

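### Does the Poisson fallback for the pulmonary exacerbation count need a stated dispersion adjustment?

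*SAP*

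**What the plan says.** SAP Section 9.3.2.2 sets the main analysis of the PEx count: "Analysis of this variable will be performed using a negative binomial regression model with a fixed effect for treatment", with baseline ppFEV1, age group and sex as covariates and log follow-up time as the offset. Protocol Section 12.3.3.1.2 agrees. The count is second in the fixed sequence of key secondary endpoints tested at 0.05 (SAP Section 9.3.2.3).

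SAP Section 7.2 ties the trial size to this endpoint: "This sample size was determined to provide adequate power for the key secondary endpoint of the number of PEX through Week 24". The sizing inputs are 0.6 events per placebo subject in 24 weeks, 10% of subjects lost, a 40% rate reduction, and a stated group size and dispersion ("with 180 subjects and the overdispersion parameter of 0.5 in each treatment group"), giving power of about 80%.

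The fallback is in Section 5.2.1, after the main SAP's appendices: "If the negative binomial regression does not converge, the analysis will be performed using the Poisson regression with the same covariates and offset". With fewer than 5 events in either group, Fisher's exact test replaces both models. The same rules extend to other counts: "Analysis of the number of PEX requiring hospitalization and/or IV antibiotics therapy, the number of planned hospitalizations for CF", and unplanned hospitalisations. The visible text gives no scale factor or robust variance for the Poisson model and does not define non-convergence.

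**The concern.** Poisson regression without a scale factor assumes that the variance equals the mean. The sponsor's own sizing assumption contradicts this: with dispersion 0.5 and a rate of 0.6, the placebo variance is 1 + 0.5 × 0.6 = 1.3 times the mean. A literal reading of Section 5.2.1 would replace a model that allows for this extra variation with one that does not. Standard errors would be too small, confidence intervals too narrow and P values too low. The PEx count drives the sample size and stands ahead of five further key secondary endpoints, so a false positive here would open the way to those tests. Leaving the variance and the trigger unstated also seems to leave two choices to whoever runs the model.

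**Working it through.** **Inputs (SAP Section 7.2).** Placebo rate 0.60, active rate 0.60 × 0.6 = 0.36, dispersion k = 0.5, 180 per arm, 10% dropout (162 per arm), two-sided 0.05.

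**1. The plan's own power.** The variance of the log rate ratio is (1/0.60 + 1/0.36 + 2 × 0.5)/162 = 5.444/162, so SE = 0.183. Power = Φ(|ln 0.6|/0.183 − 1.96) = 79.6%, in line with the stated 80%. Reading 0.5 as 1/k (so k = 2) gives 60.9%, so 0.5 is the negative binomial k.

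**2. Unscaled Poisson on every data set.** The ratio of the unscaled to the true standard error under the null is 1/√(1 + 0.5μ), and type I error is 2 × (1 − Φ(1.96 × ratio)).

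| Common rate μ | SE ratio | Type I error, formula | Simulated, unscaled | Simulated, Pearson scale floored at 1 |
|---|---|---|---|---|
| 0.60 | 0.877 | 8.6% | 8.3% | 5.1% |
| 0.48 | 0.898 | 7.8% | 7.5% | 5.0% |
| 0.36 | 0.921 | 7.1% | 6.9% | 5.0% |

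The simulations used 180 per arm, 10% with partial follow-up, no covariates and 100,000 runs per rate. At the planned effect, the SE ratio is √(4.444/5.444) = 0.904, so a nominal 95% interval covers about 92.3%. For an observed rate ratio of 0.60 the interval reads 0.43 to 0.83 instead of 0.42 to 0.86, and P is 0.002 instead of 0.005.

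**3. The analysis as planned.** The negative binomial model comes first, and Poisson only if that fit fails. The documents do not describe the software's convergence behaviour, so a fitted dispersion of zero stands in for failure. The last two columns come from 20,000 runs per rate with full negative binomial fits.

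| Common rate | Fitted dispersion zero | Error in those sets, unscaled / floored | Whole procedure as written | Whole procedure, floored scale |
|---|---|---|---|---|
| 0.60 | 0.3% (310 sets) | 5.48% / 5.48% | 5.21% | 5.21% |
| 0.48 | 1.2% (1,228 sets) | 6.60% / 6.60% | 5.27% | 5.27% |
| 0.36 | 4.5% (4,482 sets) | 6.36% / 6.22% | 5.07% | 5.05% |

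The Monte Carlo standard error of the whole-procedure figures is √(0.05 × 0.95/20,000) = 0.15 points. The within-trigger figure at 0.60 is imprecise: √(0.0548 × 0.9452/310) = 1.3 points. A repeat simulation gave 7.0/6.8/6.7% unscaled and 7.0/6.6/6.4% floored. The level moves between runs, but the scale makes almost no difference in either.

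**4. Why the scale does nothing there.** With equal follow-up and no covariates, the fitted dispersion is zero when the residual sum of squares is no larger than the event total. With 180 per arm and similar arm means, the Pearson scale is then at most about 360/358 = 1.006. The floor at 1 therefore returns almost exactly the unscaled standard error.

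**5. Failures unrelated to dispersion.** If a fraction f of data sets failed for other reasons, overall error at a rate of 0.60 would be (1 − f) × 5% + f × 8.56%. That is 5.04% for f = 1% and 5.36% for f = 10%. Both values of f are assumptions; the documents give no failure rate.

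**6. Is failure likely?** The design expects about 162 × (0.60 + 0.36) = 156 events for a five-parameter mean model (intercept, treatment and three covariates). Very sparse data go to Fisher's exact test.

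**The case for a change.** The strongest case for a change is that it costs one SAP sentence and one program option, that a floored scale can never give a smaller standard error than unscaled Poisson, and that the choice belongs in a document finalised before unblinding. Dispersion might also exceed 0.5: at a rate of 0.60, unscaled Poisson run on every data set would have an error of 12.1% for an assumed k of 1 and 18.6% for k of 2. The other event counts share the fallback and have no dispersion assumption at all.

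The cost argument stands, and so does the arithmetic for a fit that fails on clearly overdispersed data. But nothing in the documents suggests that such failures should be expected. Greater overdispersion moves the fitted dispersion away from zero, so this route to the fallback becomes rarer as the possible error grows. The small excess over 5% in the trigger sets at the two lower rates is real, but the scale leaves it nearly untouched. The hospitalisation and IV-antibiotic counts are outside the hierarchy, so only interval width is at issue there.

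The omission itself is uncertain. Section 5.2.1 carries its own numbering (5.2 in the main SAP is Secondary Objectives) and is the only section visible from that part of the file. A statement elsewhere in that part cannot be ruled out.

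**Conclusion.** The concern is right that the visible text names no variance estimator for the fallback, and right about unscaled Poisson: with k = 0.5 its standard errors are 8% to 12% too small. It does not follow that the plan needs changing. The 7.1% to 8.6% error rates belong to an analysis run on every data set, which nobody plans. As planned, PEx type I error stays near 5% with or without the scale; the largest difference in the whole-procedure simulations is 0.02 points. Even at the planned effect, the unscaled interval and P value lead to the same conclusion.

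This rests on a dispersion near 0.5, on simulations without covariates, and on zero fitted dispersion as a stand-in for non-convergence. If failures were instead unrelated to dispersion, overall error would reach 5.36% at a 10% failure rate. The model, covariates, offset, fallback and sparse-data rule are all pre-specified. What counts as non-convergence is a detail that analysts can be expected to settle sensibly in the programming.
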